#### **6.11.6. Analyses of Exploratory Objectives**

For the Insulin Treatment Satisfaction Questionnaire (ITSQ), the change from baseline to LOCF endpoint while on treatment in each domain transformed score (inconvenience, lifestyle, hypoglycemic control, glycemic control, delivery system) and overall transformed score will be analyzed using the ANCOVA model with strata (country, type of basal insulin during lead-in

period, number of prandial doses at study entry, and HbA1c stratum), and treatment as fixed effects and baseline as a covariate.

Summary statistics, including number of patients and proportion of categorical outcomes (5 levels) for the 5 dimensions (mobility, self-care, usual activity, pain/discomfort, and anxiety/depression) of the European Quality of Life – 5 Dimensions 5 Level (EQ-5D-5L) will be provided by visit and by treatment. The change from baseline to LOCF endpoint (Week 26, Visit 18) in the EQ-5D-5L United Kingdom (UK) population-based health state index score and EuroQol visual analog scale (EQ-VAS) score will be analyzed using the ANCOVA model **CCI**

For the Work Productivity and Activity Impairment Questionnaire General Health (WPAI-GH), the change from baseline to LOCF endpoint in each score (absenteeism, presenteeism, work productivity loss, and activity impairment) will be analyzed using the ANCOVA model similar to ITSQ.

Within-day and between-day glycemic variability measured by the SD and the coefficient of variation (CV) of 10-point SMBG profiles will also be analyzed by MMRM model specified in Section 6.11.5. At a given visit, the CV and SD on each day with a valid SMBG profile will be calculated using all the glucose values within that day, then the average values of these CVs and SDs will be used as the within-day CV and SD at that visit in analysis. At a given visit, the CV and SD at each of the 10 pre-specified SMBG time points will be calculated using the corresponding glucose values of the valid SMBG profiles, then the average values of these CVs and SDs will be used as the between-day CV and SD at that visit in analysis. [Table 6.3](#) lists additional variables for potential exploratory analyses.

**Table 6.3 Additional Exploratory Efficacy Variables**

Variable Description	Derivation	Statistical Method
Incremental areas under the serum glucose concentration-time curve from 0 to 30 minutes, 0 to 1 hour, 0 to 2 hours, 0 to 3 hours, and 0 to 4 hours after the meal in MMTT.	iAUC+: the total area under the serum glucose curve but above the glucose level at time 0 when the meal starts for the MMTT within the specific time frame. The area will be calculated by trapezoids rule.	ANCOVA
Area under/above the serum glucose concentration time curve from 0 to 30 minutes, 0 to 1 hour, 0 to 2 hours, 0 to 3 hours, and 0 to 4 hours after the meal in MMTT.	
 
AUC: Total area under the serum glucose curve calculated by trapezoids area within the specific time frame
 
AUC>180: Total area under the serum glucose curve but above the 180 mg/dL level within the specific time frame
 
AOC≤70: Total area above the serum glucose curve but below the 70 mg/dL level within the specific time frame.
 
	ANCOVA
Glucose variability during MMTT	
 
The CV of all serum glucose values collected during the MMTT
 
The SD of all serum glucose values collected during the MMTT.
 
	ANCOVA
1-hour and 2-hour PPG excursions by 10-point SMBG profile and daily average of the 10-point SMBG profile	
 
The difference in means between 1-hour PPG and fasting PG at the same visit
 
The difference in means between 2-hour PPG and fasting PG at the same visit.
 
The average of daily mean of the 10-point SMBG profile at the same visit
 
	MMRM
Incidence of HbA1c ≤6.5% and <7.0% without severe hypoglycemia	
 
Binary indicator with 1 indicating HbA1c ≤6.5% at Week 26 and no severe hypoglycemia during 0-26 weeks of treatment
 
Binary indicator with 1 indicating HbA1c <7% at Week 26 and no severe hypoglycemia during 0-26 weeks of treatment.
 
	Logistic regression

Abbreviations: ANCOVA = analysis of covariance; AOC = area over the curve; AUC = area under the curve; CV = coefficient of variation; iAUC = incremental area under the curve; HbA1c = hemoglobin A1c; MMTT = mixed-meal tolerance test; MMRM = mixed-effect model repeated measures; PPG = postprandial glucose; SD = standard deviation; SMBG = self-monitored blood glucose.

## 6.12. Safety Analyses

Safety measures will include AEs, hypoglycemia, vital signs and weight, treatment exposure, laboratory measures, and antibodies to insulin lispro. Refer to [Table 6.1](#) and [Table 6.2](#) for the analysis population and the baseline definition used in the analysis of a safety measurement for a specific study period.

### **6.12.1. Extent of Exposure**

Duration of exposure to study drug will be summarized. The following summary statistics will be provided: n, mean, SD, median, minimum, maximum, and sum (that is, total patient-years of exposure). The number and proportion of patients falling into the following different exposure categories will also be summarized: <1 month (>0 and <30 days), ≥1 and <3 months (≥30 and <90 days), ≥3 and <6 months (≥90 days and <180 days) and ≥6 months (≥180 days).

Patients who complete the study treatment period are required to complete a safety follow-up visit without study drug; and patients who discontinue the IP prematurely are encouraged to remain in the study without study drug. The days on study after discontinuing IP, and the days on study from date of first study drug to the last study visit date up to Visit 801 will also be summarized.

### **6.12.2. Adverse Events**

Analyses of AEs will include 2 sets of analyses, unless otherwise specified. The first set of analyses will include data collected prior to permanent discontinuation of IP. The second set of analyses will include all data collected during the course of the entire study including the follow-up visit, regardless of IP use.

Events that are newly reported after the first dose of prandial insulin provided as study drug (that is, open-label insulin lispro used during the lead-in period or IP used during the treatment period) or reported to worsen in severity from baseline (defined in [Table 6.2](#) for a specific study period) will be considered TEAEs. The MedDRA Lowest Level Term (LLT) will be used in the treatment-emergent assessment. The maximum severity for each LLT during the baseline period will be used as baseline severity. For events occurring on the day of first dose of bolus insulin provided by this study, the case report form (CRF)-collected flag will be used to determine whether the event started or worsened post-treatment.

In an overview table, the number and percentage of patients who experienced a TEAE, experienced serious adverse event (SAE), died due to an AE, discontinued from study due to an AE, discontinued IP due to an AE or TEAE related to study treatment will be summarized by treatment group .

The number and percentage of patients with TEAEs will be summarized by treatment using MedDRA PT nested within SOC. Events will be ordered by decreasing frequency within SOC. As an additional table, the percentages of patients with TEAEs will be summarized by treatment using MedDRA PT (without regard to SOC). Events will be ordered by decreasing frequency. Statistical comparisons will be applied at both the SOC and PT levels. Fisher's exact test will be performed for treatment comparison.

The number and percentage of patients with TEAEs by maximum severity will be summarized by treatment using MedDRA PT nested within SOC and data collected prior to permanent discontinuation of IP. For each patient and TEAE, the maximum severity for the MedDRA PT is the maximum postbaseline severity observed from all associated LLTs mapping to the MedDRA PT. No statistical comparison between treatment groups will be conducted.

The number and percentage of patients with common TEAEs (defined as  $\geq 5\%$  before rounding for LY900014-treated patients) will be summarized by treatment group using MedDRA PT (without regard to SOC). Events will be ordered by decreasing frequency. Treatment will be compared by Fisher's exact test.

The number and percentage of patients who experienced an SAE including deaths and SAEs temporally associated or preceding deaths will be summarized by treatment group using MedDRA PT regardless of SOC. Events will be ordered by decreasing frequency. A listing of all SAEs will also be provided.

The number and percentage of patients who discontinued from study due to an AE will be summarized by treatment group using MedDRA (without regard to SOC) using all data regardless of IP use. The number and percentage of patients who discontinued IP due to an AE will be also summarized by treatment group using MedDRA PT (without regard to SOC) using data prior to permanent discontinuation of IP. Events will be ordered by decreasing frequency. A listing of all AEs as reason for study or IP discontinuation will also be provided.

The number and percentage of patients who experienced other notable TEAEs (potential systemic hypersensitivity reaction, injection site reaction, and hepatic disorder) will be summarized by treatment group using all TEAEs regardless of IP use. For events that are gender-specific (as defined by MedDRA), the denominator and computation of the percentage will include only patients from the given gender.

Table 6.4 summarizes the planned analyses and the requirement of analysis data for different analysis periods. A 'Yes' in the IP USE column indicates that only data collected prior to permanent discontinuation of IP will be included.

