7.8.2. Special Treatment Considerations

After discontinuation of IP at the end of the treatment period or earlier, randomized patients should restart the prandial insulin used prior to study entry or transition to a rapid-acting insulin analog other than insulin lispro if the patient was not treated with insulin lispro prestudy. Patients may continue treatment with the basal insulin used during the study or return to their prestudy basal insulin at investigator discretion.

During this follow-up period, OAMs used during the study treatment period should be continued and other prestudy OAMs may be considered at investigator discretion as appropriate.

Investigators should provide patients with appropriate guidance for glucose monitoring and insulin dose adjustment throughout the follow-up period in order to maintain glycemic control.

8. Discontinuation Criteria

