**Table 6.4. Treatment-Emergent Adverse Event Analysis Periods**

Analysis Period	Analysis Population	Analysis	IP USE	Treatment
Lead-in Period	All enrolled patients	AE overview; TEAE by PT; SAE, discontinuation due to AE	N/A	Open-label insulin lispro
Treatment Period (0-26 Weeks)	All patients in safety population	AE overview; TEAE by SOC and by PT; common TEAE; TEAEs by maximum severity; SAE; IP discontinuation due to AE	Yes	LY900014, insulin lispro
Week 0 – Visit 801	All patients in safety population	AE overview; TEAE by SOC; common TEAE; SAE; other notable AEs; study discontinuation due to AE	All data regardless of IP use	LY900014, insulin lispro

Abbreviations: AE = adverse event; IP = investigational product; N/A = not applicable/available; PT = Preferred Term; SAE = serious adverse event; SOC = system organ class; TEAE = treatment-emergent adverse event.

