#### 6.12.4.3. Injection Site Reaction

The injection site reactions will be searched by MedDRA PTs from all TEAEs. The number and percentage of patients experiencing treatment-emergent injection site reaction will be summarized and compared by treatment group using Fisher's exact test.

For injection site reactions identified by MedDRA PTs, the presence and severity of erythema, induration, pain, pruritus and edema (collected on the eCRF) will be summarized for each treatment. There will be no statistical comparison between treatments.

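### The grouped comparisons of injection site and systemic hypersensitivity reactions are planned only on all data through Visit 801, with no on-IP version beside them

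*SAP*

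**What the plan says.** SAP 6.12.2 opens with a default, which Protocol 10.3.1 shares: "Analyses of AEs will include 2 sets of analyses, unless otherwise specified". It continues: "The first set of analyses will include data collected prior to permanent discontinuation of IP"; the second set takes everything through the follow-up visit.

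The same section then makes an exception for the notable TEAEs. The list starts with potential systemic hypersensitivity and ends "injection site reaction, and hepatic disorder) will be summarized by treatment group using all TEAEs regardless of IP use".

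Table 6.4 is consistent with that. Its Week 0 to Visit 801 row, on all data, reads "AE overview; TEAE by SOC; common TEAE; SAE; other notable AEs; study discontinuation due to AE". Its Treatment Period row, restricted to on-IP data, reads "AE overview; TEAE by SOC and by PT; common TEAE; TEAEs by maximum severity; SAE; IP discontinuation due to AE", with no entry for notable AEs.

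SAP 6.12.4 sends its event-specific analyses back to Table 6.4 for the data to use. SAP 6.12.4.2 defines hypersensitivity by SMQ searches plus an anaphylaxis algorithm. SAP 6.12.4.3 says: "The injection site reactions will be searched by MedDRA PTs from all TEAEs". Both compare arms by Fisher's exact test.

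On what patients take once IP has stopped, Protocol 7.8.2 says "randomized patients should restart the prandial insulin used prior to study entry or transition to a rapid-acting insulin analog other than insulin lispro", the second option being for those not on lispro before the study.

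**The concern.** LY900014 is insulin lispro reformulated with treprostinil (a local vasodilator), citrate and other excipients (Protocol 3.2). Local and hypersensitivity reactions are plausible places for the two products to differ, so a contrast restricted to time on product is of direct interest.

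The planned grouped contrast mixes time on randomized product with time on another prandial insulin. A reaction that starts after IP stops, and is new relative to the lead-in baseline, is scored to the randomized arm. A patient assigned to LY900014 who used lispro before the study goes back to lispro, so a reaction to the comparator molecule can count for LY900014. If such events arise at a similar rate in both arms, they pull the risk ratio toward 1, which is the less cautious direction for a safety question.

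**Working it through.** **Is there an on-IP version anywhere?** Setting the sections side by side:

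- SAP 6.12.2 and Table 6.4 place the notable events in the all-data set only.
- SAP 6.12.4, 6.12.4.2 and 6.12.4.3 add no on-IP set.
- The antibody-status subgroup analysis of the same reactions (SAP 6.12.7.1) also uses all data regardless of IP use.
- Table 6.2 gives TEAEs an on-IP window, and Table 6.4 uses it for SOC and PT tables with Fisher's test at both levels. The component terms are therefore compared on IP, but not the groups.

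PT tables cannot stand in for the groups. Injection site reaction is a search over several PTs. The anaphylaxis algorithm needs combinations of event categories within a patient and states no time limit, so an on-IP and a post-IP event could combine.

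**The plan's own figure, used here only for arm sizes.** The inputs in SAP 5.2 are margin 0.4, SD 1.1, and 320 vs 160 completers.

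- SE = 1.1 × √(1/320 + 1/160) = 0.1065.
- Power = Φ(0.4/0.1065 − 1.96) = Φ(1.80) = 96.4%, against 96% stated.
- 480/0.85 = 564.7, against about 564 stated. At 2:1, 564 gives 376 vs 188.

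**Off-IP share of the 30-week window (26 + 4 weeks).**

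- Completer: 4/30 = 13.3%.
- If 15% stop IP at week 13 and all stay to week 30: (0.85×4 + 0.15×17)/30 = 5.95/30 = 19.8%.

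**Effect on the comparison.** Event rates are not in the documents. The assumptions are a 26-week on-IP risk of 0.5% to 2% on lispro, a risk ratio of 2 to 5, a constant hazard λ on IP, and an off-IP hazard μ, equal in both arms, of 0, 1 or 2 times the lispro hazard.

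- Completer risk to Visit 801 = 1 − exp(−26λ − 4μ).
- With 15% stopping at week 13: 0.85 × [1 − exp(−26λ − 4μ)] + 0.15 × [1 − exp(−13λ − 17μ)].

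Worked case, 3% vs 1% on IP, μ equal to the lispro hazard:

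- μ = −ln(0.99)/26 = 0.000387 per week, and exp(−4μ) = 0.99845.
- Completers: 1 − 0.97×0.99845 = 3.15% and 1 − 0.99×0.99845 = 1.15%. The risk ratio goes from 3.00 to 2.73; the difference stays at 2.00 points.
- With early stops: on IP 2.78% vs 0.93%; all data 3.00% vs 1.15%. The risk ratio goes from 3.00 to 2.60; the difference stays at 1.85 points.

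Risk ratios at the ends of the range (lispro risk 1%):

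| On-IP ratio | Completers, μ = 1× | Completers, μ = 2× | 15% early stops, μ = 1× | 15% early stops, μ = 2× |
|---|---|---|---|---|
| 2.00 | 1.87 | 1.76 | 1.80 | 1.67 |
| 5.00 | 4.46 | 4.05 | 4.21 | 3.67 |

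The fall is about 6% to 19% in completers and 10% to 27% with early stops. The largest change in the risk difference anywhere in the grid is 7.42 to 7.36 points. With μ = 0 nothing changes.

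Exact two-sided Fisher power at 0.05, 376 vs 188, with early stops and μ equal to the lispro hazard:

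- 3% vs 1%: 21.9% on IP, 20.5% on all data.
- 5% vs 1%: 67.8% on IP, 63.2% on all data.

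**The case against.** The exception is explicit and permitted: the default applies unless otherwise specified, and the text and Table 6.4 agree, so there is no contradiction. All-data capture also has a purpose. Under SAP 6.1 the on-IP rule for adverse events ends one day after the last dose, and a reaction appearing later would be lost. Both points stand. They argue for keeping the all-data set, but not against having a second one.

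A reader might infer that these reactions are compared only on all data. The documents do not support that. The on-IP SOC and PT tables test the individual terms, and 6.12.4.2 adds a hypersensitivity summary limited to events the investigator judged related to study drug. That summary may screen out reactions to other insulin, but it rests on judgment and does not cover injection site reactions.

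A reader might also infer that the safety difference is materially diluted. The ratio is attenuated, while the absolute difference is practically unchanged. A larger effect appears if off-IP insulin is assumed to add 1 percentage point to each arm. With 5% vs 1% on IP, the ratio becomes (1 − 0.95×0.99)/(1 − 0.99×0.99) = 3.0, and Fisher power falls from 72% to 57%. But equal hazard adds only 5.95/24.05 × 1% = 0.25 point with early stops, or 4/26 × 1% = 0.15 point in completers. One full point needs an off-IP hazard about 4 times the lispro hazard (6.5 times in completers), for which the documents give no reason. Many patients return to an insulin they already used.

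Finally, safety comparison is a tertiary objective without multiplicity adjustment, and Fisher power is not a design criterion for it. That limits the severity.

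**Conclusion.** The point holds as a gap in the planned tables. The grouped injection-site and hypersensitivity endpoints have no on-IP comparison, the SAP gives no reason for departing from its two-set default, and post-IP reactions to other insulin are attributed to the randomized arm.

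Its size is modest: a risk ratio about 6% to 27% lower, 1.4 and 4.6 points of Fisher power in the two cases computed, and less than 0.1 percentage point in the risk difference. These figures rest on assumed event rates, an off-IP hazard one to two times the lispro hazard and equal in both arms, and, at the upper end, 15% stopping IP at mid-treatment and all staying to week 30. If no off-IP reactions occur, the effect is nil.

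The all-data analysis is not itself an error. The primary analysis, sample size and alpha are unaffected. This is a cheap improvement of minor severity.

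**What to change.** In SAP Table 6.4, add injection site reaction and systemic hypersensitivity reaction to the Treatment Period (0-26 Weeks) row with IP USE = Yes. Amend the notable-events sentence in 6.12.2 to match, and have 6.12.4.2 and 6.12.4.3 name both sets. Use the on-IP rule already in SAP 6.1 (last dose date + 1) and cite it, because the TEAE row of Table 6.2 ends the window at the last dose. In the on-IP set, apply the anaphylaxis algorithm only to events inside that window.

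Report this beside the Week 0 to Visit 801 analysis, which is kept in full for delayed reactions. Leave hepatic events as planned.

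The cost is a few lines of SAP text and one extra set of tables from existing searches. Reactions starting more than one day after the last dose are absent from the added set but remain in the all-data set.

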**Table 6.4. Treatment-Emergent Adverse Event Analysis Periods**

Analysis Period	Analysis Population	Analysis	IP USE	Treatment
Lead-in Period	All enrolled patients	AE overview; TEAE by PT; SAE, discontinuation due to AE	N/A	Open-label insulin lispro
Treatment Period (0-26 Weeks)	All patients in safety population	AE overview; TEAE by SOC and by PT; common TEAE; TEAEs by maximum severity; SAE; IP discontinuation due to AE	Yes	LY900014, insulin lispro
Week 0 – Visit 801	All patients in safety population	AE overview; TEAE by SOC; common TEAE; SAE; other notable AEs; study discontinuation due to AE	All data regardless of IP use	LY900014, insulin lispro

Abbreviations: AE = adverse event; IP = investigational product; N/A = not applicable/available; PT = Preferred Term; SAE = serious adverse event; SOC = system organ class; TEAE = treatment-emergent adverse event.

### 6.12.3. Deaths

The listing of all deaths by patient for all enrolled patients will be provided as part of the SAE listing, regardless of the investigator's or the sponsor's judgment about causality. Each listing will include study ID, investigator ID, patient ID, treatment group, baseline age, sex, associated AE, first and last dose date for open label insulin lispro and randomized IP, and the event date.

### 6.12.4. Hypoglycemic Events and Other Adverse Events

The analysis plan for the following AEs are discussed in Section 6.12.4.1 through Section 6.12.4.4:

- hypoglycemic events
- systemic hypersensitivity reaction
- injection site reaction
- hepatobiliary events

All these AE analyses will be similar to the TEAE analyses, refer to Table 6.4 for the requirement of analysis data for a specific analysis period.

#### 6.12.4.1. Hypoglycemic Events

Hypoglycemia events that occur during the study outside the MMTT will be captured using an paper diary starting from Visit 2 through Visit 801. Whenever hypoglycemia is suspected, the patient should record the blood glucose value, any associated symptoms, and the treatment administered in paper diary. A set of events is counted as 1 event in analysis if it consists of an originating event and subsequent continuing events as marked by the patient in paper diary, or the duration between adjacent events is  $\leq 30$  minutes. The event with the highest severity will be selected for analysis with severity determined in the order of: 1) it is a severe hypoglycemia, 2) it has symptoms of hypoglycemia reported, and 3) it has the lowest blood glucose value. If there are multiple events tied in all 3 aspects, the event with the largest number of non-missing responses to the questions of nocturnal hypoglycemia and postmeal time frame will be selected. If there are still multiple events tied, the latest event (based on data entry time) will be selected.

The following types of hypoglycemia events will be derived in the analysis data sets: documented hypoglycemia, severe hypoglycemia and nocturnal hypoglycemia. Only severe hypoglycemia will be collected as AEs and all episodes of severe hypoglycemia will be considered as SAEs. Documented hypoglycemia (including documented symptomatic hypoglycemia, documented asymptomatic hypoglycemia and documented unspecified hypoglycemia) will be based on blood glucose (BG)  $\leq 70$  mg/dL. In addition, documented clinically significant hypoglycemia with similar criterion as above documented hypoglycemia except for the threshold of BG  $< 54$  mg/dL will be summarized.

Table 6.5 provides detailed statistical methods for each endpoint related to hypoglycemia. For these analyses, hypoglycemia events prior to the discontinuation of IP will be summarized. Additional analyses for other types of hypoglycemic events not mentioned in the table and for the post-treatment period may be conducted as needed.

The incidence and number of episodes of hypoglycemia during the MMTT will be summarized by treatment and time relative to the meal ( $\leq 0.5$ ,  $\leq 1$ ,  $\leq 2$ ,  $\leq 4$ ,  $>1$  to  $\leq 2$  and  $>2$  to  $\leq 4$  hours after start of the meal) and analyzed by Fisher's exact test.

A listing of patients with at least 1 severe hypoglycemia reported (as SAE) after randomization will be provided. Summary of severe hypoglycemia treatment and outcome from the patient diary will be provided.

A list of MedDRA PTs will be used for the narrow search of potential severe hypoglycemia in spontaneously reported AEs. The events identified through the search strategy that are also reported as SAEs will be summarized and compared between treatments. Fisher's exact test will be used to assess the treatment difference in the proportion of patients with potential severe hypoglycemia.

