- **Relative hypoglycemia:** An event during which typical symptoms of hypoglycemia occur, that does not require the assistance of another person and is accompanied by BG >70 mg/dL (3.9 mmol/L).
- **Probable symptomatic hypoglycemia:** Symptoms of hypoglycemia were present, but BG measurement was not reported.
- **Overall hypoglycemia:** This optional category combines most cases of hypoglycemia (documented hypoglycemia and probable symptomatic hypoglycemia, including severe hypoglycemia). It does not include relative hypoglycemia. Nocturnal and severe hypoglycemia are special cases of documented or probable hypoglycemia. If an event of hypoglycemia falls into multiple subcategories, that event should only be counted once in the category of overall hypoglycemia.

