
 
To compare LY900014 and insulin lispro with respect to the incidence and rate of documented symptomatic postmeal hypoglycemia
 
	
 
Rate (events/patient/year and/or events/patient/30 days) and incidence (percent of patients with at least 1 event) of documented symptomatic postmeal hypoglycemia within 1 and 2 hours after start of a meal from baseline through Week 26
 

 
To compare LY900014 and insulin lispro with respect to the incidence and rate of documented symptomatic hypoglycemia
 
	
 
Rate (events/patient/year and/or events/patient/30 days) and incidence (percent of patients with at least 1 event) of documented symptomatic hypoglycemic events from baseline through Week 26
 

 
To compare LY900014 and insulin lispro with respect to 1,5-AG
 
	
 
Change from baseline in 1,5-AG values at Week 26
 

 
To compare LY900014 and insulin lispro with respect to 10-point SMBG profiles
 
	
 
Change from baseline in 10-point SMBG values at Week 26
 

 
To compare LY900014 and insulin lispro with respect to total, basal, and prandial insulin dose
 
	
 
Change from baseline in total, basal and prandial insulin dose and prandial/total insulin dose ratio at Week 26
 

--	---

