**Summary of Analyses for Endpoints Related to Hypoglycemia**

Endpoint	Analysis Period	Statistical Method
Rate of severe hypoglycemic events (per patient per year / 100 years)	0-12, 0-26, 12-26 weeks	Exposure adjusted rate per year / 100 years (calculated by total number of events divided by total exposure for individual patients) will be provided and the empirical method (see Appendix 1 for details) will be used for treatment comparison.

Endpoint	Analysis Period	Statistical Method
Incidence of severe hypoglycemic events	0-12, 0-26, 12-26 weeks	Proportion of patients with severe hypoglycemia will be reported. The treatment comparison will be based on a logistic regression model with treatment as an independent variable.

a All documented hypoglycemia and the subcategories based on the thresholds of blood glucose  $\leq 70$  mg/dL and blood glucose  $< 54$  mg/dL will be analyzed, except for postmeal hypoglycemia for which only the threshold of  $\leq 70$  mg/dL will be applied.

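### Keeping one diary record per merged hypoglycemia episode can drop or downgrade documented low-glucose episodes and date some postmeal episodes too late

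*SAP*

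**What the plan says.** SAP 6.12.4.1 has two merging rules. Under the first, which relies on the patient's own marking, "A set of events is counted as 1 event in analysis if it consists of an originating event and subsequent continuing events". Under the second, records are merged when "the duration between adjacent events is" 30 minutes or less. One record then represents the set. The rule for choosing it reads "severity determined in the order of: 1) it is a severe hypoglycemia, 2) it has symptoms of hypoglycemia reported, and 3", where the third criterion is the lowest BG. Ties on all three go to the record with most answers to the nocturnal and postmeal questions. If a tie remains, "the latest event (based on data entry time) will be selected".

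The next paragraph of the section derives the categories: documented at BG 70 mg/dL or less, and clinically significant below 54 mg/dL. Footnote a to SAP Table 6.5 applies both cut-offs: "All documented hypoglycemia and the subcategories based on the thresholds of blood glucose" of 70 and 54 mg/dL are analyzed, except that postmeal events use 70 only. SAP Table 4.1 lists documented symptomatic hypoglycemia and "documented symptomatic postmeal hypoglycemia within 1 and 2 hours after start of a meal" among the other secondary endpoints.

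Protocol 9.4.1 recognizes low readings without symptoms or without symptom information, symptoms with BG above 70 (relative hypoglycemia), symptoms with no BG (probable symptomatic), and severe events for which glucose may be unavailable.

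**The concern.** Documented hypoglycemia is defined by glucose, but glucose comes third in choosing the record to be analyzed. Nothing in the SAP carries the lowest BG of the set, or the time of its first qualifying record, over to the kept record. A low reading can therefore be discarded with its record, and an episode can take the time of a later record.

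At stake are the All Documented, nocturnal and non-nocturnal counts at both thresholds, and the placing of events in the postmeal windows. Timing matters here because Protocol 3.2 expects the faster insulin to reduce late postprandial hypoglycemia.

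**Working it through.** **No figure to reproduce.** Neither document gives the share of merged episodes or an expected hypoglycemia rate. The check applies the selection rule as written to constructed sets.

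**Order of operations.** The SAP describes merging and selection first and categories second. The tie-break that favours records with answered nocturnal and postmeal questions makes sense only if the kept record's own fields are analyzed. Selecting first is the natural reading, though the SAP does not state it outright.

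**Enumeration.** Take non-severe records with 3 symptom states (yes, no, no information) and 7 BG values (48, 50, 60, 65, 75, 80, missing). That gives 21 record types and 21² = 441 ordered pairs. Missing BG ranks last.

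- Pairs with a reading of 70 or less: 12 record types qualify and 9 do not, so 441 − 9² = 360. Status is lost when a symptomatic record at 75, 80 or missing (3) beats a non-symptomatic record of 70 or less (2 × 4 = 8): 3 × 8 × 2 orders = **48 of 360**.
- Pairs with a reading below 54: 441 − 15² = 216. Status is lost when a symptomatic record at 60, 65, 75, 80 or missing (5) beats a non-symptomatic 48 or 50 (2 × 2 = 4): 5 × 4 × 2 = **40 of 216**. Of these, 2 × 4 × 2 = 16 remain in the 70 mg/dL count and 24 leave both.
- Pairs with one record that is both symptomatic and 70 or less: 441 − 17² = 152, of which **0** are lost. Below 54: 441 − 19² = 80, of which **0** are lost. This holds for sets of any size without a severe record, because the lowest BG among the symptomatic records is kept.

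The SAP does not say how a missing BG ranks. If it ranked as lowest, the losses would be 88 of 360 and 60 of 216, and for documented symptomatic 8 of 152 and 4 of 80.

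**Worked sets** (BG in mg/dL, minutes after meal start):

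| Records | Kept | Effect |
|---|---|---|
| Symptomatic 72 at 50; asymptomatic 62 at 65 | 72 | Lost from documented at 70 |
| Symptomatic, no BG, at 50; no symptom information, 62 at 65 | No-BG record | Lost from documented at 70 |
| Symptomatic 64 at 50; no symptom information, 50 at 65 | 64 | Lost below 54, stays at 70 |
| Symptomatic 66 at 50; symptomatic 58 at 75 | 58 at 75 | Moves from ≤1 h to >1 to ≤2 h |
| Symptomatic 66 at 105; symptomatic 60 at 130 | 60 at 130 | Moves from ≤2 h to >2 to ≤4 h |
| Symptomatic 68, 66, 63, 60 at 50, 75, 100, 125 | 60 at 125 | Moves from ≤1 h to >2 to ≤4 h |
| Control: symptomatic 60 at 50; symptomatic 66 at 70 | 60 at 50 | No change |

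In the first set the kept record is relative hypoglycemia. It also leaves the protocol's overall category, of which Protocol 9.4.1 says "It does not include relative hypoglycemia". That category is optional there, is absent from SAP Table 6.5, and is used in the SAP for the antibody subgroup analysis.

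In the timing rows every record is symptomatic, so the shift comes from lowest-BG selection and not from the symptom rank. The fourth row stays within 2 hours of the meal; the fifth and sixth leave that window.

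**Illustrative size (assumed inputs).** If 2% to 20% of episodes are merged sets and 10% to 50% of those are misclassified, the share affected is 0.02 × 0.10 = 0.2% to 0.20 × 0.50 = 10%. Equal loss in both arms leaves a rate ratio unchanged. Assumed losses of 5% against 3% multiply it by 0.95/0.97 = 0.979, and 10% against 5% by 0.90/0.95 = 0.947.

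**The case against.** The strongest defence is that symptom-first ranking protects the secondary endpoint, which needs symptoms and low glucose in the same record. That stands: within the limits shown above, no such episode is lost. Ranking glucose first would turn some symptomatic episodes into asymptomatic ones. A reader might infer that the documented symptomatic endpoint is under-counted; the rule as written does not support that.

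Second, the SAP does not say outright that merging precedes the threshold filter. Merging within each category would remove the threshold losses. This also stands, and it makes the point conditional on the order in which the section is written.

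Third, the rule is identical in both double-blind arms. A reader might infer a biased treatment comparison. The documents give nothing from which a difference in loss could be derived, so that remains a possibility only.

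Fourth, a reader might take the final tie-break to push event times later. It picks the latest record by data entry time, not event time, and applies only after ties on severity, symptoms, BG and answered questions. No systematic delay follows from it.

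Finally, when the early record has no symptoms, dating a symptomatic event by its symptomatic record is consistent with the endpoint. The timing point is therefore limited to sets in which an earlier record already met the definition.

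**Conclusion.** The point holds as a specification defect. If the section is followed in its written order, some merged episodes with a reading of 70 or less, or below 54, are dropped from the All Documented, nocturnal or non-nocturnal counts, or are downgraded. Some documented symptomatic postmeal episodes are placed in a later window than their first qualifying record. Single-record events are unaffected. So are the threshold categories of sets whose lowest BG lies on a symptomatic record, provided the set has no severe record and a missing BG does not rank as lowest.

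The size in this trial is unknown. The 48 of 360 and 40 of 216 are shares of constructed patterns, and the 0.2% to 10% range rests wholly on assumed inputs. The documented symptomatic count is exposed only through missing-BG ranking or a severe record without BG. A distorted comparison between arms is not shown.

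**What to change.** Revise SAP 6.12.4.1 as follows.

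- Merge records into episodes first and say so. Then count the episode once in each category (documented at 70 or less, documented below 54, documented symptomatic, severe, nocturnal, non-nocturnal) if any single record in the set meets that category's full definition.
- Do not combine the BG of one record with the symptoms of another. In the enumeration, lowest BG plus any symptom would create documented symptomatic episodes that no record shows, in 48 patterns at 70 and 40 below 54. That would change a secondary endpoint.
- Take the postmeal window from the earliest record in the set that meets the category definition.
- State that a missing BG never ranks as lowest.

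The cost is SAP wording and a few lines of derivation code; no new data are needed. Documented and below-54 counts may rise slightly. One episode may appear in more than one subcategory, for example asymptomatic below 54 and symptomatic at 70 or less, so the tables should note that subcategories need not sum to the total.
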